## 4.3.14.1.2 Presentation

Duration of exposure to Investigational Products (IP)(s) in weeks and cycles are summarised by descriptive statistics and by frequency. Dose intensity is summarised by descriptive statistics. Exposure to IP(s) i.e. total amount of study drug received is listed for all subjects. Exposure swimmer plot(s) are produced, with a line presented for each subject to display relevant exposure and disposition details.

Dosing deviations for IP(s) are summarised with reasons for deviations for the following categories: delays, reductions, and interruptions. Dosing delays are derived based on the scheduled dosing dates using the previous dose given as reference. The number and percentage of subjects with dosing delays and total dose delays per subject are summarised.

## 4.3.14.2 Adverse Events

## 4.3.14.2.1 Definitions and Derivations

The Medical Dictionary for Regulatory Activities (MedDRA) (version 25 or higher) is used to code the AEs. AEs are graded according to the National Cancer Institute Common Terminology Criteria for AEs (CTCAE) (version 5.0).

Treatment emergent adverse events (TEAEs) are all AEs which onset or worsen in severity following the first administration of IP in Cycle 0 within the duration of the treatment period, up to and including 30 days after the last dose of study treatment for ceralasertib monotherapy or 90 days after last dose of study treatment for ceralasertib and durvalumab combination. Worsening in severity is determined by comparison with the pre-treatment CTCAE grade of the AE recorded closest to the start of dosing.

AEs with a missing start time or where time is not collected, which occur on the same day as first IP administration, are reported as treatment emergent.

For rules on missing or partial dates, see Section 3.4.6.

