#### 4.3.12.2 Adverse Events

# 4.3.12.2.1 Definitions and Derivations

The Medical Dictionary for Regulatory Activities (MedDRA) (version 25 or higher) is used to code the AEs. AEs are graded according to the National Cancer Institute Common Terminology Criteria for AEs (CTCAE) (version 5.0).

Treatment emergent adverse events (TEAEs) are all AEs which onset or worsen in severity following the first administration of IP within the duration of the treatment period, up to

and including 30 days after the last dose of study treatment for ceralasertib monotherapy or 90 days after last dose of study treatment for ceralasertib and durvalumab combination, and prior to the start of any subsequent anti-cancer therapy,. Worsening in severity is determined by comparison with the pre-treatment CTCAE grade of the AE recorded closest to the start of dosing.

AEs with a missing start time or where time is not collected, which occur on the same day as first IP administration, are reported as treatment emergent.

For rules on missing or partial dates, see Section 3.4.6.

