# 3.2.4 On-treatment

For the purposes of summarizing safety data assessed at visits, in addition to baseline data, only on-treatment data are included in the summary tables. On-treatment data is defined as data on/after the first dose of study treatment (including Cycle 0) and with assessment date up to and including the date of last study treatment + 90 days (safety follow-up), and prior to the start of any subsequent anti-cancer therapy.

For biomarker data the on-treatment assessment is strictly defined as Cycle 0 Day 7. The Cycle 0 Days 15 – Day 28 period will be defined as off-treatment.

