#### 4.3.14.5.2 Presentation

Vital signs are summarised by study visit which includes descriptive statistics for the value of the parameters and the changes from baseline. Absolute values and change from baseline for vital signs data at each timepoint are presented using box plots.

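### The sub-study's definition of treatment-emergent adverse events does not stop at new anti-cancer therapy, and its follow-up length for ceralasertib-only subjects differs from the on-treatment window in the same SAP

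*SAP*

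**What the plan says.** Sub-study SAP, section 4.3.14.2.1, counts adverse events as treatment emergent from the first Cycle 0 dose until "30 days after the last dose of study treatment for ceralasertib monotherapy or 90 days after last dose of study treatment for ceralasertib" with durvalumab. The sentence then closes without mentioning subsequent therapy: "90 days after last dose of study treatment for ceralasertib and durvalumab combination. Worsening in severity" is how it runs into the next one.

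Sub-study SAP, section 3.2.4, sets the window for another class of safety output: "For the purposes of summarizing safety data assessed at visits, in addition to baseline data, only on-treatment data are included in the summary tables". That window ends at "the date of last study treatment + 90 days (safety follow-up), and prior to the start of any subsequent anti-cancer therapy", with no separate length for ceralasertib alone. Vital signs fall under it, because section 4.3.14.5.2 states "Vital signs are summarised by study visit".

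In the main-study SAP, sections 3.2.4 and 4.3.12.2.1 agree with each other. Both use 30 days for monotherapy and 90 for the combination, and both restrict to data "prior to the start of any subsequent anti-cancer therapy".

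Sub-study section 4.3.14.3.2 presents laboratory abnormalities from the start of study drug until the final on-study assessment, with neither a day limit nor a stop at new therapy.

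**The concern.** The sub-study TEAE sentence is close to the main-study sentence with the last clause missing, and no reason is given for leaving it out. Section 4.3.14.2.2 builds the overall, SOC/PT and severity tables on this definition, and SAEs are summarised the same way. A subject who comes off study drug and starts another agent within 90 days keeps contributing to those all-cause tables while exposed to the new agent. Visit-based safety data for the same subject stop when that agent starts.

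The 30-day figure raises a second problem. The sub-study has one group: ceralasertib alone in Cycle 0, then the combination (section 3.2.2). It has no monotherapy arm, and the term is not defined for it. A programmer must decide who gets 30 days, and will find that section 3.2.4 gives the same people 90.

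**Working it through.** The plan gives no figure to reproduce. The check sets the definitions side by side.

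| Source | Length after last dose | Stops at new therapy? |
|---|---|---|
| Sub-study 4.3.14.2.1 (TEAE) | 30 days ceralasertib alone / 90 days combination | No |
| Sub-study 3.2.4 (visit-based safety) | 90 days for all | Yes |
| Main 4.3.12.2.1 (TEAE) | 30 / 90 days | Yes |
| Main 3.2.4 (visit-based safety) | 30 / 90 days | Yes |
| Sub-study 4.3.14.3.2 (laboratory abnormalities) | Final on-study assessment | No |

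**Subsequent therapy.** Among the TEAE and on-treatment definitions, only the sub-study TEAE row lacks the stop. Let t be the days from last dose to new therapy, with t < 90, in a subject who received the combination. Visit-based data stop at day t, while TEAEs continue for up to 90 - t further days. The SAP does not give t, so a range is assumed:

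- t = 14: 90 - 14 = 76 days
- t = 21: 90 - 21 = 69 days
- t = 60: 90 - 60 = 30 days

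These are days of window, not counts of events or subjects.

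**Ceralasertib-only subjects.** The TEAE window is counted from the last dose of study treatment. The monotherapy length can therefore matter only for someone whose last dose came before any durvalumab. The plan foresees such subjects: section 4.2.1.2 tabulates those who did not receive durvalumab. The mismatch for them is 90 - 30 = 60 days. With a last dose on Cycle 0 Day 7, TEAEs end on Day 7 + 30 = 37, and visit-based data on Day 7 + 90 = 97.

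**Which side departs from the main SAP.** The main SAP uses 30 days for ceralasertib monotherapy in both of its definitions. The sub-study TEAE length matches that, and the flat 90 days in sub-study section 3.2.4 does not. On the subsequent-therapy clause it is the reverse: section 3.2.4 matches and 4.3.14.2.1 does not.

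**Laboratory data.** The visit-based laboratory summaries follow section 3.2.4. The abnormality tables (worst grade, grade 3-4 rates, grade shifts) follow their own rule. The main SAP has the same rule in 4.3.12.3.2, so this third window is not peculiar to the sub-study.

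**The case against.** Adverse events are not visit-based data, and section 3.2.4 limits itself to visit-based summaries. A different window for each is not a contradiction in itself. That is fair, but the main SAP aligns the two and the sub-study gives no reason to depart.

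It can also be said that counting later events is conservative and that attribution limits any misreading, since section 4.3.14.2.2 plans IP-related tables and splits by causal relationship. This helps the attributed tables but not the all-cause TEAE and SAE tables. Nor is the definition consistently the more inclusive one: for ceralasertib-only subjects it is the shorter of the two.

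No pooling or formal safety comparison with the main study is described, so the departure from Arm 1's rule matters only to someone reading the two reports together. Section 3.2.5 assigns visits only as far as the last-dose visit, which leaves unclear how much of the 90 days the by-visit summaries would fill. How adverse events are collected after new therapy starts is a matter for the protocol. These points limit the practical effect but leave the conflicting definitions in place.

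A reader might infer three stronger things that the SAP does not support:

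- That laboratory data as a whole stop at new therapy. The abnormality tables do not.
- That events on days 31 to 90 in ceralasertib-only subjects are lost. If recorded, they leave the TEAE tables but stay in the listing of non-treatment-emergent events, and deaths are summarised and listed for all subjects.
- That a fixed share of the follow-up window is contaminated. Any such share rests on a single assumed t.

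**Conclusion.** The sub-study SAP is wrong as written on one clause and inconsistent on one length. Followed literally, its TEAE and SAE tables can include events that arise under next-line therapy, for up to 76 to 30 days per affected subject at assumed starts of 14 to 60 days after last dose. Subjects who never receive durvalumab have two windows 60 days apart. How many subjects either point touches cannot be derived from the document.

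The sub-study plans for about 30 subjects with paired evaluable biopsies, and its primary endpoint is CD8+ T-cell infiltration. No primary result, test or decision rule is affected. It should be corrected before the safety tables are programmed, because the text leaves the programmer to choose.

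**What to change.** These are changes to analysis windows only.

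1. In sub-study 4.3.14.2.1, restrict the TEAE definition to events "prior to the start of any subsequent anti-cancer therapy", as main SAP 4.3.12.2.1 does, or state why the sub-study differs. Events after new therapy stay in the non-treatment-emergent listing already planned in 4.3.14.2.2.
2. Replace the undefined monotherapy category with a definition that fits a single-group study (subjects who never receive durvalumab), and state one analysis follow-up length for them in both 3.2.4 and 4.3.14.2.1.
3. Reconcile the laboratory abnormality window in 4.3.14.3.2 with these, or say that it is deliberately longer.

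The cost is a few lines of text and one flag in the adverse-event dataset. Section 3.2.8 already has rules for partial start dates of subsequent anti-cancer therapy, so no further data are needed.

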#### SAEs

A serious adverse event (SAE) is any AE that:

- Results in death
- Is immediately life-threatening
- Requires inpatient hospitalisation or prolongation of existing hospitalisation
- Results in persistent or significant disability/incapacity.
- Is a congenital anomaly/birth defect in offspring of the subject
- Is an important medical event that may jeopardize the subject.

#### **Adverse Events of Special Interest (AESI)**

Adverse events of special interests are events of scientific and medical interest specific to the further understanding of ceralasertib and durvalumab safety profile and require close monitoring and rapid communication by the investigators to AstraZeneca. An AESI can be serious or non-serious. All AESIs will be recorded in the eCRF. Additionally, AESI will be identified programmatically using a definition file maintained by Astra Zeneca.

Adverse events of special interests for durvalumab include but are not limited to events with a potential inflammatory or immune-mediated mechanism and which may require more frequent monitoring and/or interventions such as steroids, immunosuppressants and/or hormone replacement therapy. An immune-mediated AE is defined as an AESI that is associated with drug exposure and is consistent with an immune-mediated mechanism of action and where there is no clear alternate aetiology.

If the investigator has any questions in regards to an event being an immune-mediated AE, the investigator should promptly contact the AstraZeneca study physician or clinical lead.

Adverse events of special interests/ immune-mediated AE observed with anti-PD-L/PD-1 agents such as durvalumab include pneumonitis, hepatitis, diarrhoea/colitis, intestinal perforation, endocrinopathies (hypo- and hyperthyroidism, adrenal insufficiency, hypophysitis/hypopituitarism and Type 1 diabetes mellitus), nephritis, rash/dermatitis, myocarditis, myositis/polymyositis, pancreatitis and rare/less frequent events (including, but not limited to haematological events, neuromuscular toxicities [such as myasthenia gravis and Guillain-Barré syndrome], non-infectious encephalitis, non-infectious meningitis, pericarditis, rheumatological events, sarcoidosis, skin events, uveitis [and other events involving the eye] and vasculitis).

In addition, infusion-related reactions and hypersensitivity/anaphylactic reactions with a different underlying pharmacological aetiology are also considered AESIs.

More detailed guidelines for their evaluation and treatment are described in detail in the Dose Modification and Toxicity Management Guidelines (version 28-Oct-2021). These guidelines have been prepared by the sponsor to assist the investigator in the exercise of his/her clinical judgement in treating these types of toxicities. These guidelines apply to AEs considered causally related to the study treatment/study regimen by the reporting investigator.

There are no currently identified AESI for Ceralasertib but if any are identified, these will be reported in similar/appropriate outputs to the durvalumab AESI.

#### Other significant adverse events (OAE)

During the evaluation of the AE data as part of the monthly offline listing review process, an AstraZeneca medically qualified expert reviews the list of AEs that were not reported as SAEs and AEs leading to discontinuation of study treatment after Parexel's review took place. Based on the expert's judgement, adverse events of particular clinical importance may, after consultation with the Global Safety Physician, be considered OAEs and reported as such in the CSR. A similar review of laboratory values, vital signs, ECGs and other safety assessments are performed for identification of other significant adverse events. This review takes place prior to database lock, and any AEs identified are fully documented in meeting minutes. Further review following database lock may result in ad-hoc OAEs being identified, in this case, the OAEs and resulting summaries are fully documented in the CSR.

Examples of these are marked haematological and other laboratory abnormalities, and certain events that lead to intervention (other than those already classified as serious), dose reduction or significant additional treatment.

#### 4.3.14.2.2 Presentation

All TEAEs will be summarised and listed. AEs which are not treatment emergent will be listed for the Safety analysis set and will be listed individually by subject.

TEAEs will be counted once for each subject for calculating percentages of subjects experiencing TEAE. In addition, if the same TEAE occurs multiple times within a particular subject, the highest severity and level of relationship observed will be reported. For tables by MedDRA system organ class (SOC) and MedDRA preferred term (PT), subjects with multiple TEAEs will be counted once for each SOC/PT.

An overall summary table of the number of subjects experiencing each category of adverse event will be produced. The number of subjects experiencing treatment emergent adverse events by MedDRA SOC and PT will be summarised and incidence rates will be provided.

Severity and relationship to IP will be summarised. Further splits by CTCAE grade, causal relationship to IP and adverse events with Grade 3-4 will be also summarised.

Separate tables will present adverse events leading to discontinuation, serious adverse events, IP-related adverse events, and other significant adverse events.

Details of any deaths will be summarised and listed for all subjects. AEs leading to death will also summarised.

## SAEs

SAEs are summarised as described above for the TEAEs.

## AEs of special interest

Grouped summary tables of certain MedDRA preferred terms are produced and may also show the individual preferred terms which constitute each AESI grouping. These groupings may be defined using MedDRA terms, SMQs (standardized MedDRA queries) and PTs (preferred terms). Groupings are provided by the coding team prior to DBL, and a listing of the preferred terms in each grouping is provided. Summaries of the above-mentioned grouped AE categories include number and percentage (%) of subjects who have:

- At least one AESI presented by event outcome
- At least one AESI causally related to IP
- At least one AESI leading to discontinuation of study treatment.

A summary of total duration (days) of AESI are provided for events which have an end date and this may be supported by summaries of ongoing AESIs at death and, separately, at data cut-off.

## 4.3.14.3 Clinical Laboratory, Blood Samples

## 4.3.14.3.1 Definitions and Derivations

Laboratory tests are grouped according to chemistry and haematology. Laboratory parameters are assessed at baseline as well as throughout the study.

For chemistry and haematology parameters, laboratory abnormalities with toxicity grades according to the NCI CTCAE version 5.0 are derived.

Change from baseline in haematology and clinical chemistry endpoints is calculated for each post-dose visit. CTC grades are calculated at each visit. Maximum post-baseline CTC are also calculated. Absolute values are compared to the local laboratory reference range and classified as low (below range), normal (within range or on limits of range) and high (above range). All values classified as high or low are flagged on the listings.

#### **Liver Function Parameters**

Subjects with elevated post-baseline alanine aminotransferase (ALT), aspartate aminotransferase (AST) or Total Bilirubin that fall into these categories are identified.

Liver Function Parameters	Category	
ALT	• $\geq 3 \times - \leq 5 \times \text{ULN}$	
AST	• $\geq 3 \times - \leq 5 \times \text{ULN}$	
Total bilirubin	• $>3 \times -\leq 5 \times ULN$	
ALT or AST	• $\geq 3 \times - \leq 5 \times \text{ULN}$	
Potential Hy's law	• (AST $\ge$ 3 × ULN or ALT $\ge$ 3 × ULN) and (Total Bilirubin $\ge$ 2×ULN) a	

**Table 7 Liver Function Parameters** 

ULN: upper limit of normal range.

a It includes all subjects who have ALT or AST $\geq$ 3xULN and total bilirubin (BILI)  $\geq$ 2xULN, and in which the elevation in transaminases precede or coincide with (that is, on the same day as) the elevation in BILI.

#### 4.3.14.3.2 Presentation

The change in each laboratory parameter from baseline to each post-baseline visit are summarised graphically.

Laboratory abnormalities occurring from the start of IP administration to the last assessment on study are presented. Worst toxicity grade, rates of grade 3-4 toxicity, and grade shifts of 2 or more from baseline to the maximum grade are presented. Summaries indicating hyper- and hypo- directionality of change are produced, where appropriate. Laboratory parameters that cannot be graded via NCI CTCAE are summarised with frequencies of post-baseline laboratory values categorized as low (L), normal (N), or high (H) using laboratory normal ranges comparing to baseline.

Listings are provided for all laboratory results.

#### **Liver Function Parameters**

Number and percentage of subjects with elevated post-baseline ALT, AST or Total Bilirubin (BILI) are tabulated. Individual subject data with elevated ALT or AST plus BILI falling into the "Potential Hy's law" are summarised and listed.

## 4.3.14.4 Clinical Laboratory, Urinalysis

#### 4.3.14.4.1 Definitions and Derivations

Change from baseline in urinalysis endpoints are calculated for each post-dose visit. CTC grades are calculated at each visit. Maximum post-baseline CTC is also calculated. Absolute values are compared to the local laboratory reference range and classified as low (below range), normal (within range or on limits of range) and high (above range). All values classified as high or low are flagged in the listings.

#### 4.3.14.4.2 Presentation

Listings are provided for urinalysis. Urinalysis endpoints are summarised by study visit which will include descriptive statistics for the value of the parameters and the changes from baseline. Absolute values and change from baseline at each timepoint are presented. Maximum post-baseline CTC grades which are not normal will be summarized.

For urinalysis, shift from baseline to worst on treatment results are presented.

#### 4.3.14.5 Vital Signs

#### 4.3.14.5.1 Definitions and Derivations

Vital signs (weight, body temperature, systolic and diastolic blood pressure, respiratory rate and heart [pulse] rate) are performed at timepoints as specified in the schedule of assessments. Any changes in vital signs should be recorded as an AE if applicable.

#### 4.3.14.5.2 Presentation

Vital signs are summarised by study visit which includes descriptive statistics for the value of the parameters and the changes from baseline. Absolute values and change from baseline for vital signs data at each timepoint are presented using box plots.

## 4.3.14.6 Electrocardiogram

## 4.3.14.6.1 Definitions and Derivations

Electrocardiogram (ECG) parameters are assessed in triplicate at baseline and subsequent triplicate measurements and should only be taken if clinically indicated. Single ECG readings are collected at visits other than baseline. ECG parameters include: PR, RR, QRS, QT, and QTcF. The QTcF is considered as the primary correction method to assess subject cardiac safety.

From these resting 12-lead ECGs values of the QT and RR intervals and the QT interval corrected for heart rate using Fridericia's correction (QTcF) is derived using the following formula:

•  $QTcF = QT/RR^{(1/3)}$  where RR is in seconds

The values of QTcF (milliseconds) are re-derived from the values of RR and QT during the creation of the reporting database.

#### 4.3.14.6.2 Presentation

ECG parameters are listed.

#### 4.3.14.7 Echocardiogram/Multigated Acquisition

#### 4.3.14.7.1 Definitions and Derivations

An echocardiogram or Multigated Acquisition (MUGA) scan to assess left ventricular ejection fraction (LVEF) will be performed at the visits screening and treatment discontinuation and as clinically indicated.

#### 4.3.14.7.2 Presentation

LVEF will be listed.

#### 4.3.14.8 Bleeding events

Information obtained by the bleeding event questionnaires is depicted in a listing.

# 4.4 Exploratory Analyses

# 4.5 Pharmacokinetics

Plasma concentrations-time data are not analysed to determine the PK parameters. Pre-dose and post-dose plasma concentrations for each scheduled time-point are summarised, PK Day and Cycle using appropriate descriptive statistics. PK concentration data are listed for each subject in the safety analysis set.

Individual concentrations may be excluded from summary tables, graphical or statistical analysis for legitimate scientific reasons. Any exclusions, together with justification for the exclusion, is clearly documented in the CSR. These individual data are still presented in the listings, but are flagged to identify that they are excluded from summary outputs.

The following descriptive statistics are presented for plasma concentrations:

• n

